CooperVision™

PROTOCOL

**DAILY DISPOSABLE DISPENSING CLINICAL TRIAL OF NEPTUNE LENS
AGAINST MYDAY LENS**

Sponsor Study Code: CV-16-60
Version Number: 2.3
Implementation document Date: 31 AUG 2016
Sponsor Company: CooperVision, Inc.
Study Category: Design Validation
Clinical Sites: CORL, Indiana University
TOSI, University of Houston

Protocol Sponsor:

[Redacted]

Date

[Redacted]

[Redacted]

Site Principal Investigator:

[Redacted]

Date:

[Redacted]

[Redacted]

Site Principal Investigator:

[Redacted]

Date:

[Redacted]

TABLE OF CONTENTS

1	Introduction	5
2	Study Objective	5
2.1	Study Hypothesis	5
3	Study Design	5
4	Ethics Review / Statement of Compliance	6
4.1	Relevant Standards / Guidelines	6
4.2	Institutional Review Board	6
4.3	Informed Consent	7
5	Clinical Trial Registration	7
6	Potential Risks and Benefits to Human Subjects	7
7	Materials and Methods	8
7.1	Subjects.....	8
7.2	Number of Sites.....	9
7.3	Study Materials.....	9
7.4	Visit Schedule and Procedures.....	12
8	Adverse Event Reporting	20
8.1	Adverse Event Definitions.....	20
8.2	Procedures for Adverse Events	22
8.3	Reporting Adverse Events	23
8.4	Discontinuation from the Study	23
9	Device Malfunctions	24
10	Statistical Analysis	24
10.1	Sample Size Calculation.....	24
10.2	Statistical Analysis	25
11	Data Quality Assurance	25
11.1	Study monitoring.....	25
11.2	Sponsor Responsibilities	26
11.3	Investigator Responsibilities	26
11.4	Record keeping	27
11.5	Record retention	27
12	Protocol Deviations	28
12.1	Major protocol deviations.....	28
12.2	Minor protocol deviations.....	28
13	Data Entry / Data Management	29
13.1	Confidentiality	29

13.2Publication.....	29
14 Study Costs	29
15 Study Report	29
16 Appendix	30
16.1Appendix 1	30
16.2Appendix 2	31
16.3Appendix 3	33

1 Introduction

CooperVision is evaluating the clinical performance of MyDay 1-Day lenses (Neptune test lenses)

[REDACTED]

2 Study Objective

The purpose of this study is to investigate the overall clinical performance of the Neptune daily disposable silicone hydrogel lens (test) compared to the MyDay lens (control).

This is a study to validate the performance of Neptune lenses when worn on a daily disposable wear modality over 1 month (for each lens).

The primary variables of interest are:

- Comfort (subjective ratings)
- Vision (logMAR, high and low illumination, and subjective ratings)
- Anterior ocular health (corneal staining, conjunctival staining and hyperemia)

Secondary variables are:

- Lens fit performance
- Handling (subjective ratings)
- Lens surface wettability and deposit resistance

- [REDACTED]
- Dryness
- [REDACTED]

3 Study Design

This will be, prospective, multicenter, double-masked, randomized, bilateral, 1 month cross-over, dispensing study comparing the Neptune test lens against the MyDay control lens with a study duration of approximately two months.

Each subject will be randomized to wear either the test or control as a matched pair first and subjects will be randomized based on the order in which the subject is enrolled and qualified into the study.

Both test and control lenses will be used in a daily disposable lens wear modality for one (1) month. It is anticipated that this study will involve 5 scheduled visits:

- Visit 1: Enrollment/ Screening/ Baseline/Fitting/Dispensing of first pair of lens
- Visit 2: 1-week follow-up visit (Day 7±3)
- Visit 3: 4-week follow-up visit for the first pair and dispensing visit of the second pair of contact lenses (Day 28±4)
- Visit 4: 1-week follow-up visit of second pair (Day 7±3 from dispense of second pair)
- Visit 5: 4-week follow-up for the second pair and exit visit (Day 28±4 from dispense of second pair)
- Subjective questionnaires will be collected at the following timepoints:
 - Contact Lens Dry Eye Questionnaire-8 (CLDEQ-8) at baseline,
 - Dispensing/visit 1: Baseline and dispensing questionnaires,
 - Visits 2 and 4: One week questionnaire, and
 - Visits 3 and 5: One month questionnaire

Visits that fall outside of the specified visit windows or repeat visits within the window will be classified as unscheduled visits for analysis purposes.

4 Ethics Review / Statement of Compliance

4.1 Relevant Standards / Guidelines

This implementation document has been developed in accordance with the following:

- ISO 14155 Clinical Investigation of Medical Devices for Human Subjects, Parts 1 & 2
- ICH Harmonized Tripartite Guideline for Good Clinical Practice
- Declaration of Helsinki

4.2 Institutional Review Board

This study will be conducted in accordance with Institutional Review Board regulations (U.S. 21CFR Part 56.103) or applicable IEC regulations. Copies of all IRB/IEC correspondence with the investigator/sponsor will be kept on file.

[figure not shown]
[figure not shown]
[figure not shown]
The conduct of this study will occur at two sites, TOSI at the University of Houston and CORL at Indiana University. The conduct of this study will be approved for each site by an Institutional Review Board prior to commencement.

4.3 Informed Consent

Informed consent shall be obtained in writing from the subject and the process shall be documented before any procedure specific to the clinical investigation is carried out.

5 Clinical Trial Registration

This study will be registered in the clinical trials registry (www.ClinicalTrials.gov or equivalent) by the study sponsor.

7 Materials and Methods

7.1 Subjects

This study will recruit at two clinical sites, The Ocular Surface Institute (TOSI) at the University of Houston, and the Clinical Optics Research Lab (CORL) at Indiana University. Up to 70 participants will be dispensed across both sites with the aim of completing study products to 60 participants across both sites.

Potential participants will be identified from the investigators' clinic database records and/or will be actively recruited by advertisements circulated at the investigational sites as approved by the appropriate IRB.

There are no provisions for replacing subjects who are discontinued from the study.

Each subject will be given a unique ID number. Additionally, all subjects must meet the study inclusion and exclusion criteria listed below.

Inclusion criteria

A person is eligible for inclusion in the study if he/she:

- Has had a self-reported oculo-visual examination in the last two years.
- Is at least 18 years of age and has full legal capacity to volunteer.
- Has read and understood the information consent letter.
- Is willing and able to follow instructions and maintain the appointment schedule.
- Is correctable to a visual acuity of 20/40 or better (in each eye) with their habitual vision correction or 20/20 best-corrected.
- Must achieve 20/30 or better (in each eye) with study lenses
- Requires spectacle lens powers between -0.75 and -6.50 diopters sphere (0.25D steps).
- Has no more than 0.75 diopters of refractive astigmatism.
- Currently wears soft contact lenses.
- Have clear corneas and no active ocular disease.
- Has not worn lenses for at least 12 hours before the examination

Exclusion Criteria

A person will be excluded from the study if he/she:

- Has never worn contact lenses before.
- Has any systemic disease affecting ocular health.
- Is using any systemic or topical medications that will affect ocular health.
- Has any ocular pathology or severe insufficiency of lacrimal secretion (moderate to severe dry eyes) that would affect the wearing of contact lenses.

- Has persistent, clinically significant corneal or conjunctival staining using sodium fluorescein dye.
- Has any clinically significant lid or conjunctival abnormalities, active neovascularization or any central corneal scars.
- Is aphakic.
- Has undergone corneal refractive surgery.
- Is pregnant, lactating, or planning a pregnancy at the time of enrolment (by verbal confirmation at the screening visit).
- Have taken part in any other contact lens or care solution clinical trial or research, within one week prior to starting this study.

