7.4.1 Baseline Visit

Procedures to be Performed

The following evaluations will be performed to assess eligibility according to the Inclusion and Exclusion Criteria at the baseline visit only:

- The patient is expected to attend the baseline visit not wearing their habitual contact lens products.
- The subject will be required to read and sign an Informed Consent Form prior to enrolment. When the subject has signed the consent form, the subject will be considered to be enrolled on to the study.
- Subject demographics and medical history (age, sex, race and ethnicity, medical conditions, medications, allergies)
- Contact lens history (own lens information, rewetting drop use, and wear time)

[REDACTED]

[REDACTED]

[REDACTED]

[REDACTED]

[REDACTED]

[REDACTED]

[REDACTED]

[REDACTED]

- Baseline visual acuity with spectacles or spectacle refraction (logMAR).
- Auto refraction/auto keratometry: Horizontal and Vertical K readings (D)
- Sphero-cylindrical refraction (D), and best sphere refraction (D) & monocular & binocular distance visual acuity (high contrast) (logMAR)
- Slit lamp biomicroscopy will be assessed according to the approved study biomicroscopy CRF (Appendix 3).
- The investigator will confirm that the patient meets the criteria set out in the inclusion criteria, and is eligible to continue in the study.

[REDACTED]

- The subject will be assigned a randomization ID and the first pair of contact lenses (either test or control) will be selected according to the randomization table (Appendix 2).

- Initial contact lens power chosen based on vertexed, spherical equivalent obtained from refraction. When the desired power is not available, subjects can be fitted with lenses within +/-0.25 of their required contact lens powers. The uncorrected amount will be kept the same for both test and control/s.
- The lenses will be inserted by the subject from the blister pack as described in 7.3.3.
- The lens fit will be assessed for fit acceptance (acceptable or not acceptable) and absence of lens defects. If the fit is acceptable and there are no defects, the subject will be allowed to sit for 10 minutes to allow for the lenses to settle.
- Monocular over refraction will be done to determine if a different power is needed.

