8.4 Discontinuation from the Study

A subject's study participation may be discontinued at any time if, in the opinion of the sponsor or the investigator it is in the best interest of the subject. All discontinuations will be fully documented on the appropriate study forms and the Discontinuation Form will be completed.

Subjects will be discontinued at the discretion of the investigator, sponsor or subject. The following is a list of possible reasons for discontinuation from the study:

- Screening failure: Subjects will be discontinued if they do not meet the inclusion and exclusion criteria outlined in section 4.2.1.
- Unacceptable performance with products to be used in study: Subjects may be discontinued if they are unable to achieve acceptable comfort and /or vision with the study products.
- Positive slit lamp finding: Subjects may be permanently discontinued from the study depending on the severity of the condition and on the judgement of the investigator.
- Adverse event: If a subject experiences an adverse event during the study they may be discontinued based on the clinical judgement of the investigator.
- Symptoms: If the subject has persistent symptoms they may be discontinued based on the clinical judgement of the investigator.
- Disinterest, relocation or illness: The subject may choose to discontinue due to reasons within or beyond their control.

- Violation of protocol or non-compliance: The subject will be discontinued if they are unable or unwilling to follow the protocol specified visit schedules and/or study procedures.
- Instillation of topical ocular medication: The subject will be discontinued if they elect to use a topical ocular medication during the study unless that topical ocular medication is prescribed for a limited duration (less than two weeks) to treat a transient condition; in this case the subject may remain an active subject (at the discretion of the investigator) after stopping topical ocular medication following resolution of the ocular condition).
- Lost to follow-up: The subject will be discontinued if they cannot be contacted and does not return for a final exit visit, and if the investigator has made a reasonable effort to contact the subject for a final study visit.
- Premature termination of the study by the sponsor, the clinical sites or the Office of Research Ethics at the sites.

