10.2 Statistical Analysis

Statistical analysis and report writing will be performed by the sponsor. De-identified data will be provided to the sponsor by each site for the sponsor to perform the analyses. Each site will only have access to the data collected at their site.

Statistical analyses will be conducted on all randomized subjects who have successfully completed the study without a protocol deviation that may be regarded as impacting the assessments of primary hypothesis. The overall type I error rate will set at $\alpha=5\%$ level. All primary hypotheses must be met in order to satisfy the objective of the study.

Descriptive statistics will be generated at baseline/dispense and each follow up visits (e.g. mean, SD). In each case, Noninferiority will be concluded if the low limit of 95% confidence interval of difference in subjective response is above the low bound: -10. Paired testing, ANOVA, or mixed linear model may also be used for additional analysis on selected variables. Binomial test was used to analysis the results for the count data of subjective preferences; the number of "no preference" were evenly distributed to the two options on the basis they would be equally likely to choose either. A p-value less than or equal to 0.050 will be regarded as statistically significant.

11 Data Quality Assurance

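### The 20/30 criterion with study lenses can, on the visible text, be checked only after randomization, so lens-dependent vision failures can leave the completers-only analysis uncounted

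*Combined protocol and SAP*

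**What the plan says.** Section 7.1 has two acuity criteria. One needs no study lens: "Is correctable to a visual acuity of 20/40 or better (in each eye) with their habitual vision correction or 20/20 best-corrected". The other does: "Must achieve 20/30 or better (in each eye) with study lenses".

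Section 3 states that "subjects will be randomized based on the order in which the subject is enrolled and qualified into the study". In 7.4.1 the visible steps run in this order: refraction and baseline acuity, slit lamp, confirmation of eligibility, a redacted block, and then "The subject will be assigned a randomization ID and the first pair of contact lenses (either test or control) will be selected" from the randomization table. Insertion, settling, over-refraction and acuity with the lens come after that. Under 7.4.3 the second pair is first inserted at Visit 3 (Day 24 to 32). Section 7.4.1 introduces the eligibility evaluations as belonging to the baseline visit only, and Table 2 in 7.4.5 ticks eligibility only in the Baseline column.

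Under the screening-failure heading, 8.4 says: "Subjects will be discontinued if they do not meet the inclusion and exclusion criteria outlined in section 4.2.1". The criteria are in fact in 7.1. A separate item in 8.4 allows, but does not require, discontinuation for unacceptable comfort or vision with the study products.

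Section 10.2 defines the analysis set: "Statistical analyses will be conducted on all randomized subjects who have successfully completed the study without a protocol deviation" that may bear on the primary hypothesis. Section 7.1 makes no provision for replacing discontinued subjects. Section 2 names vision, both logMAR acuity and subjective ratings, among the primary variables.

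**The concern.** An inclusion criterion should be settled before allocation. This one is an early reading of a primary variable on the lens that randomization has just assigned. If the two lenses differ in acuity, who stays in depends on which lens came first. A subject removed at fitting contributes nothing to the vision comparison, and is also lost to comfort and ocular health.

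What is at stake is mainly information. Poor acuity with a lens is what a validation of overall clinical performance should report. Here it can be filed as a screening failure and never appear as a result for the lens that produced it.

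**Working it through.** **1. Order of events.** The argument rests on sequence, so the sections are set side by side.

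| Step | Section | Is acuity with a study lens known? |
|---|---|---|
| Eligibility confirmed | 7.4.1 | No, for either lens |
| Randomization ID and first pair assigned | 7.4.1 | No |
| First pair inserted, over-refracted, acuity read | 7.4.1 | First lens only |
| Second pair inserted | 7.4.3, Visit 3 | Second lens, after about four weeks |

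On the visible text the criterion cannot be checked when eligibility is confirmed. The requirement in section 3 that subjects be qualified when randomized cannot be met for it.

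**2. The plan's own enrolment figure.** 60/(1 − 0.10) = 66.7 and 60/(1 − 0.15) = 70.6, so about 70 is consistent with 10.1. No separate allowance is made for removal at 20/30. If a share f is removed on top of dropout d, completers are 70 × (1 − d) × (1 − f). For f = 5% this gives 70 × 0.90 × 0.95 = 59.9 and 70 × 0.85 × 0.95 = 56.5. Power is not the issue: with the difference of 10 and SD of 15 in Table 3, a paired t-test needs 20 subjects for 80% power.

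**3. Size of the selection effect.** The documents give no acuity mean, SD, correlation or failure rate. Assumed inputs:
- mean −0.02 logMAR on control and SD 0.10;
- same-eye correlation between lenses 0.7 and between-eye correlation 0.4 (variance shares 0.4 subject, 0.3 eye, 0.3 residual);
- cut-off log10(30/20) = 0.176, taken as 0.18;
- a subject fails a lens if either eye is worse than the cut-off;
- half the subjects start on each lens.

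Simulated results with the test lens 0.05 logMAR worse:

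| | Fail on test | Fail on control | Mean difference |
|---|---|---|---|
| All randomized | 11.9% | 4.3% | 0.050 |
| Retained, first pair screened | 5.0% | 0.8% | 0.049 |
| Retained, both pairs screened | none | none | 0.047 |

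In subjects, for 70 randomized and first-pair screening:
- True failures: 70 × 0.119 = 8.3 on test and 70 × 0.043 = 3.0 on control.
- Removed: 35 × 0.119 + 35 × 0.043 = 4.2 + 1.5 = 5.7, leaving 64.3.
- Failures still visible: 64.3 × 0.050 = 3.2 on test and 64.3 × 0.008 = 0.5 on control.
- The gap in failure rates falls from 11.9 − 4.3 = 7.6 points to 5.0 − 0.8 = 4.2 points.

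With the test lens 0.10 worse, 26.4% fail on test and 4.3% on control. The mean difference becomes 0.098 with first-pair screening and 0.093 with both. With equal lenses the bias is zero.

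**4. Sensitivity.** A simpler model, with one acuity value per subject and lens, control mean 0.00, SD 0.08 to 0.10 and correlation 0.5 to 0.8, gives the same picture. A true 0.050 becomes 0.047 to 0.049 (first pair) or 0.044 to 0.048 (both). A true 0.100 becomes 0.094 to 0.098 or 0.084 to 0.095.

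**The case against.** **Every failure is deleted.** A reader might infer that the analysed failure rate must be 0% on both lenses. The documents do not support that. Eligibility is assessed at baseline only, and nothing says that 20/30 is re-applied at Visit 3 or at follow-up, where acuity is read again and stays in the data. The second pair fits the discretionary clause in 8.4 better than the screening-failure clause. The both-pairs row above is therefore an upper case. The first-pair case still stands, as does discretionary removal on either lens.

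**It tilts a non-inferiority test.** A reader might also infer a bias toward non-inferiority on acuity. The only margin in 10.2 is −10 on subjective response, and none is given for logMAR. No effect on a subjective rating has been shown.

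**The lenses are nearly the same.** Table 1 gives both the same material, water content, base curve, diameter and power range. Astigmatism is capped at 0.75 D, and over-refraction comes before the acuity reading. Failures may well be few, and some would reflect the eye rather than the lens, since 7.1 admits subjects correctable only to 20/40 with their habitual correction. This limits the size of the effect. It does not settle how failures are handled.

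**A check may be hidden.** The redacted block in 7.4.1 lies exactly between eligibility confirmation and randomization, so a lens trial there cannot be excluded. The visible text points the other way, because the first pair is taken from the randomization table and only then inserted.

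**The completers-only set is the deeper problem.** That is fair. The 20/30 criterion is one route into it, but one that selects directly on a primary variable.

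**Conclusion.** The point holds, with moderate confidence because of the redaction. Following the visible plan removes randomized subjects according to acuity on the first assigned lens, allows removal for poor vision on either lens, and then omits them from the analysis. If the lenses differ, this hides part of the difference in vision failures.

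The effect on the mean is small: 0.050 to 0.049 or 0.047 under the assumed inputs, and nothing if the lenses are equal. The effect on counted failures is larger, with about 8 test-lens failures in 70 reduced to about 3 visible ones when only the first pair is screened and the test lens is 0.05 logMAR worse. All of these figures rest on assumed acuity inputs; the true failure rate is unknown. The change should be made, but the point does not show that the trial's conclusion would be wrong.

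**What to change.** 1. Reconcile 7.1, 7.4.1, Table 2 and 8.4 on when, and for which pair, the 20/30 criterion applies. Whatever admits a subject to randomization should rest on measurements taken before it. Section 7.4.1 already records "best sphere refraction (D) & monocular & binocular distance visual acuity (high contrast) (logMAR") at baseline; the text should say which refraction that acuity belongs to. Correct the reference in 8.4 to section 4.2.1.
2. In 10.2, keep every randomized and dispensed subject, counting the Visit 1 fitting as dispensing, in an all-randomized analysis with the data available. The mixed linear model that 10.2 already mentions can use subjects with data on one lens only.
3. Report acuity worse than 20/30 as a vision outcome by lens, with the number who wore each lens as the denominator. Do not class these subjects as screening failures for analysis.

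Whether such a subject continues lens wear remains a clinical decision under 8.4, and this point does not ask for the acuity threshold itself to change.

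The cost is protocol and analysis wording, slightly more analysis work, and a vision result that may look less favourable.

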7.1.1 Repeated Screenings

In some circumstances a repeated screening may need to be scheduled. Examples include, but are not limited to:

- a) Incomplete information available at time of screening to determine eligibility (e.g. current lens brands worn, history from current eye care practitioner etc.)
- b) Study procedures unable to be completed in time scheduled for visit;
- c) Study products not available at the time of the screening visit;
- d) A transient health condition which may affect the eye(s) (e.g. a common cold, active allergies, fatigue etc.)
- e) The short term use of medications (e.g. antibiotics, antihistamines etc.)
- f) Reassessment of baseline ocular conditions (e.g. corneal and/or conjunctival staining, scars etc.)

The maximum total number of screenings permitted will be 3.

